## 6. STUDY PROCEDURES

### 6.1. Data Source

Patients using apixaban will be identified from the National Prescribed Drug Register (PDR) which contains information on all drugs prescribed in Sweden that are dispensed to patients outside hospitals, including information about patients, drugs by ATC codes, dates, settings of the dispensing, and the specialty of the prescribing physician.

Relevant clinical history for the apixaban users identified from the PDR will be obtained from the National Patient Register (NPR). Patients in the PDR who have used apixaban will be linked to the NPR by a personal identification number (PIN) unique to all Swedish citizens. The NPR contains data from all hospital admissions in Sweden from 1987 to present. At each discharge, information is collected about the patient's demographics, primary and secondary diagnoses, procedure codes, hospitals and wards of admission, and dates of admission and discharge. Patients who have undergone knee or hip replacement surgery will be identified by applicable procedure codes and relevant ICD-10 diagnostic codes. The ICD-10 classification system was used from 1997 and onwards so data on diagnoses and procedures may extend back to 1997.

Since 2001, it is also possible to collect the same information from visits to hospital outpatient offices. Information about other diagnoses (eg, atrial fibrillation) in patients admitted to the hospitals without knee or hip replacement or visiting hospital outpatient offices will also be retrieved. The register is updated annually and data from the previous year is usually available for analyses in November each year after completion of data quality checks.

The databases cover the whole Swedish population of 9.3 million inhabitants. In 2008, about 14,500 knee and hip replacement surgeries and 4,600 hemi-hip arthroplasties were performed; 78% of the procedures were performed for primary arthrosis. The number of primary TKA was 10,600 in 2008. In addition, re-operations and revisions were also performed. Following an average hospital stay of 4 days, 25% of the patients are discharged to rehabilitation centers or nursing homes and 75% of the patients are discharged to home. The total number of hip arthroplasties increased by 10% from 2008 to 2010.

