### **6.3. Decision Rule for Defining On- and Off-label Use**

For the purpose of this study, apixaban prescriptions for the NVAF and treatment of DVT/PE indications will be considered off-label up to and including the date that apixaban received approval for those uses in the EU. Apixaban prescriptions for the NVAF and the treatment of DVT/PE indications will be classified as on-label starting on the day after regulatory approval and continuing through the end of the study.

On-label use of apixaban will be defined as a dispensation of the drug to:

1. An adult (ie, 18 years of age or older) and
2. A patient whose hospital records include:
  - a) An elective hip or knee replacement within 30 days before the apixaban prescription, or,
  - b) An apixaban prescription after 19 November 2012 and a diagnosis of NVAF before that apixaban prescription, or,
  - c) An apixaban prescription after 28 July 2014 and a diagnosis of DVT or PE before the apixaban prescription ([Figure 1](#)).

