#### 6.4. Data Elements

- Patient demographics: Age and Gender.
- Information on prescription for apixaban: dispensing date, dose, amount dispensed, duration of use based on amount of drug prescribed, refill date, and repeat prescription.
- Hospital admission information: dates of hospital admission and discharges, ICD-10 diagnosis codes in discharge diagnoses, surgical procedure codes.
- Outpatient hospital office visit information: date of visit, ICD-10 diagnosis codes, department type.
- Primary care records in Västra Götaland County (see above): date of contact, contact type (visit, telephone), ICD-10 diagnosis codes.
- Other recently dispensed drugs: ATC code, dispensing date, dose, amount dispensed, use at the time of apixaban dispensing based on amount of drug prescribed.

The operational definitions and coding scheme of the variables will be described in the statistical analysis plan.

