## 7.2. Data Analyses

Descriptive analyses of patient level data will be conducted. Patients will be classified as on-label or off-label apixaban users based on their first prescription for apixaban. The demographic and clinical characteristics of patients identified to have received an apixaban dispensation will be described. The proportion of patients receiving the drug for indications within and outside the approved label in each of the study years will be estimated and any trend over time will be described. From the hospital discharge records, the comorbidities and clinical procedures (e.g., surgeries) at the time of or within 30 days prior to the off-label use will be tabulated as the possible indications for the off-label use. If discharge records during this period do not provide possible indications, information from previous discharges will also be tabulated according to the most recent diagnosis. Furthermore, possible switching from other antithrombotic treatment will be investigated based on dispensed prescriptions during the past year. The dose and duration of prescriptions will be summarized where available.

Stratified descriptive analyses by indication will be performed as described below. As the first step, the study will estimate the proportions of all patients in Swedish databases over the 3-years post-launch period who received apixaban for:

1. VTE prevention following elective hip and knee replacement surgery (on-label indication).
2. NVAf (off-label indication before the approval, and on-label following the approval).
3. Treatment of DVT/PE (off-label indication before the approval, and on-label following the approval).
4. Any other conditions from a list of pre-defined off-label indications, including other types of surgery and history of other diseases (off-label indications). These may include but will not be limited to hip fracture surgeries, general surgeries, gynaecologic and abdominal surgeries, and diagnoses such as cancer, myocardial infarctions, other cardiac conditions, and other hypercoagulable states in which apixaban could be used off-label.

5. Patients who have no evidence of the conditions for on-label use and who cannot be assigned to the list of pre-defined off-label uses will be classified as off-label and unknown.

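### Section 6.3 requires the NVAF or DVT/PE diagnosis to fall before the apixaban prescription, so a first diagnosis dated on the index day counts as off-label and inflates the off-label proportion

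*Protocol*

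**What the plan says.** Section 6.3 of the protocol sets the classification rule. For atrial fibrillation it asks for "An apixaban prescription after 19 November 2012 and a diagnosis of NVAF before that apixaban prescription", and for venous thromboembolism "An apixaban prescription after 28 July 2014 and a diagnosis of DVT or PE before the apixaban prescription". Neither criterion mentions a diagnosis on the same day, and neither says which hospital date dates an inpatient diagnosis. The same section does settle another boundary day explicitly: the approval date itself is assigned to off-label use, and on-label use starts the day after.

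The unit being classified is introduced differently: "On-label use of apixaban will be defined as a dispensation of the drug to" an adult who meets one of the criteria. The criteria themselves then run from the prescription.

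Section 7.2 fixes the index event: "Patients will be classified as on-label or off-label apixaban users based on their first prescription for apixaban".

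On the dates available:

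- Section 6.4 lists, for the drug, "Information on prescription for apixaban: dispensing date, dose, amount dispensed, duration of use based on amount of drug prescribed, refill date, and repeat prescription". No prescribing date is listed.
- Section 6.4 also lists admission and discharge dates for hospital stays, and visit dates for hospital outpatient contacts.
- Section 6.1 says of the patient register: "At each discharge, information is collected about the patient's demographics, primary and secondary diagnoses, procedure codes", along with ward and stay dates.

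Section 7.2 also describes how possible reasons for off-label use are tabulated from discharge records. There the window includes conditions present when use starts as well as those in the preceding 30 days.

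**The concern.** Objective 1 is the proportion of users treated for an approved indication. A patient may be diagnosed and given a prescription on one date, and may collect the drug that day. With day-level dates such a diagnosis is not before the prescription. If the patient has no earlier qualifying record, criteria (b) and (c) fail. Because only the first prescription counts, no later refill can correct the classification, and the patient enters the off-label group.

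The two sides of the classification are also handled unevenly. An NVAF diagnosis dated on the discharge day, with the drug dispensed that same day, can fail the on-label rule. It can then appear in the section 7.2 tabulation as a possible reason for off-label use, although NVAF is by then an approved indication.

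The anchor is unsettled as well. A surgery or approval date close to its limit can fall on either side, depending on whether prescribing or dispensing is taken as the index.

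**Working it through.** **Step 1: who fails the rule.** Compare diagnosis date and index date for a patient who has an approved indication on the index day and no earlier qualifying record.

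| First qualifying diagnosis | Index day | Result under *before* |
|---|---|---|
| Outpatient visit, earlier day | later | passes |
| Outpatient visit, same day | same | fails |
| Inpatient, dated by discharge, dispensed after discharge day | later | passes |
| Inpatient, dated by discharge, dispensed on discharge day | same | fails |
| Inpatient, dated by admission on an earlier day | later | passes |

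The exposed group is therefore mainly same-day cases. The register holds only drugs dispensed outside hospital (section 6.1), so a fill after a stay normally falls on or after the discharge date.

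**Step 2: effect of the missing prescribing date.** Dispensing cannot come before prescribing. Using the dispensing date as index can only move the index later, which makes an earlier diagnosis more likely. The mixed wording therefore does not produce the upward bias. It does affect boundaries: surgery 28 days before prescribing but 32 days before dispensing meets the 30-day window on one anchor and misses it on the other.

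**Step 3: reproduce the protocol's precision.** Inputs are N = 19,000 and the off-label shares in Table 2. Full width = 2 × 1.96 × √(p(1 − p)/N).

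| p | Computed width (points) | Table 2 |
|---|---|---|
| 5% | 0.62 | 0.6 |
| 15% | 1.02 | 1.0 |
| 25% | 1.23 | 1.2 |
| 35% | 1.36 | 1.4 |
| 45% | 1.42 | 1.4 |

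Table 2 is reproduced; the Wilson interval gives the same widths. These widths cover sampling error only.

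**Step 4: scale of the bias.** Let p be the true off-label share and f the share of truly on-label patients counted as off-label. Observed share = p + (1 − p)f, so the shift is (1 − p)f. The protocol does not give f. The values below are assumptions, at p = 25%, where 0.75 × 19,000 = 14,250 patients are truly on-label.

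| Assumed f | Patients moved | Observed off-label | Shift (points) |
|---|---|---|---|
| 0.5% | 71 | 25.4% | 0.37 |
| 1% | 142 | 25.75% | 0.75 |
| 2% | 285 | 26.5% | 1.50 |
| 5% | 713 | 28.75% | 3.75 |
| 10% | 1,425 | 32.5% | 7.50 |

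**Step 5: break-even.** The shift equals the CI half-width when f = half-width/(1 − p).

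- p = 25%: 0.62/0.75, about 0.8%
- p = 15%: 0.51/0.85, about 0.6%
- p = 5%: 0.31/0.95, about 0.3%

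**The case against.** The strongest reply is that this belongs in the SAP. Section 6.4 leaves operational definitions and coding to that document, which is not at hand, and the treatment of same-day records is usual SAP content. Figure 1, to which section 6.3 refers, is also not shown. This stands in part: the SAP may set date conventions. But the word *before* is in the protocol's own decision rule, in a section that settles a boundary day in words when it means to. An SAP that follows the rule inherits the problem; one that departs from it contradicts section 6.3.

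A second reply is that a diagnosis leading to a prescription at one visit does come before it in the ordinary sense. That is a fair reading of intent, but the listed data carry dates and not times, so the rule cannot be applied that way without saying that same-day records count.

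Third, the section 7.2 window only describes patients already classed as off-label. Section 6.3 sets no look-back limit for NVAF or DVT/PE, and records may reach back to 1997, so in that respect the on-label rule is generous. This stands. It limits the exposed group to patients with no earlier qualifying record; it does not help those patients.

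A reader might infer something stronger: that newly diagnosed patients in general become off-label, because diagnoses are registered at discharge and only a dispensing date is held. The documents do not support that. Dispensing is outside hospital, outpatient diagnoses are dated by visit, admission dates are available, and a dispensing index works in the opposite direction.

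**Conclusion.** The point holds for a limited group. Read as written, criteria (b) and (c) class as off-label a patient whose first qualifying diagnosis is dated on the index day. The error is one-directional and falls on the objective 1 estimate.

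Its size cannot be computed from the protocol. What can be said is that the margin is small. At 25% true off-label use, about 0.8% of on-label patients (0.0082 × 14,250, about 117 people) is enough to exceed the half-width of about 0.62 points. This assumes N = 19,000 as in Table 2 and misclassification in one direction only. A reader might be tempted to apply a round share to the projection of up to 13,000 AF patients and quote a bias of several points. No source in the document supports such a share, or the idea that same-day diagnosis is the usual pattern.

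The mixed use of dispensation and prescription is a separate ambiguity. It matters for the surgery window and the approval cut-offs, and it does not cause the upward bias.

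**What to change.** 1. In section 6.3, name the first dispensing date as the single index date. Use it for the diagnosis criteria, the 30-day surgery window and the approval cut-offs, and align section 6.2 and, where needed, Figure 1.
2. In criteria (b) and (c), replace *before* with *on or before*.
3. Count an inpatient diagnosis when the stay began on or before the index date. Keep procedures at their own date where one is recorded, because dating surgery by admission would distort the 30-day window.
4. Report a sensitivity analysis that dates inpatient diagnoses by discharge.

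The cost is wording plus one additional classification run; the dispensing, admission, discharge and visit dates are already listed in section 6.4. The small downside is that a few diagnoses first made later in a stay still open at the index date would count as on-label. The sensitivity analysis shows how much this matters.

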**Figure 1: Flow Chart for Record linkage and On and Off-label Classification.**

090177e1868a5a5e\Approved\Approved On: 22-May-2015 13:30

If during the study apixaban receives approval for any other condition in Sweden, the new indication will be considered on-label use following the date of approval.

#### 6.4. Data Elements

- Patient demographics: Age and Gender.
- Information on prescription for apixaban: dispensing date, dose, amount dispensed, duration of use based on amount of drug prescribed, refill date, and repeat prescription.
- Hospital admission information: dates of hospital admission and discharges, ICD-10 diagnosis codes in discharge diagnoses, surgical procedure codes.
- Outpatient hospital office visit information: date of visit, ICD-10 diagnosis codes, department type.
- Primary care records in Västra Götaland County (see above): date of contact, contact type (visit, telephone), ICD-10 diagnosis codes.
- Other recently dispensed drugs: ATC code, dispensing date, dose, amount dispensed, use at the time of apixaban dispensing based on amount of drug prescribed.

The operational definitions and coding scheme of the variables will be described in the statistical analysis plan.

### 7. DATA ANALYSIS/STATISTICAL METHODS

The variables to be collected in this study will be documented in a Statistical Analysis Plan. This document may modify the plans outlined in the protocol; however, any major modifications will be reflected in a protocol amendment.

#### 7.1. Sample Size Calculation

This is a descriptive study of drug usage without any pre-defined hypothesis to be tested. Therefore, no power calculation was performed. All individual patients identified to have received apixaban in the database in the study period will be included in the study without any sampling procedure.

Based on the Sponsor's projection of the number of patients using apixaban in 2012-2014 for prevention of VTE following a hip or knee replacement it is expected that approximately 600 patients will be included in the study. It is projected that up to 13,000 patients with atrial fibrillation (AF) may be included in the study.

As shown in the table below, 19,000 apixaban patients with any indication will provide sufficiently precise estimates of on-label use. For instance, if 25% of patients use apixaban off label, the width of the 95% CI for the off-label use percent will be 1.2 percent ([Table 2](#)).

**Table 2: Precision Around the Off Label Use Proportion Estimates Assuming a Total Sample Size of 19,000 Patients**

Off label use (%)	Width of 95% CI for off label use (%)
5	0.6
15	1.0
25	1.2
35	1.4
45	1.4

## 7.2. Data Analyses

Descriptive analyses of patient level data will be conducted. Patients will be classified as on-label or off-label apixaban users based on their first prescription for apixaban. The demographic and clinical characteristics of patients identified to have received an apixaban dispensation will be described. The proportion of patients receiving the drug for indications within and outside the approved label in each of the study years will be estimated and any trend over time will be described. From the hospital discharge records, the comorbidities and clinical procedures (e.g., surgeries) at the time of or within 30 days prior to the off-label use will be tabulated as the possible indications for the off-label use. If discharge records during this period do not provide possible indications, information from previous discharges will also be tabulated according to the most recent diagnosis. Furthermore, possible switching from other antithrombotic treatment will be investigated based on dispensed prescriptions during the past year. The dose and duration of prescriptions will be summarized where available.

Stratified descriptive analyses by indication will be performed as described below. As the first step, the study will estimate the proportions of all patients in Swedish databases over the 3-years post-launch period who received apixaban for:

1. VTE prevention following elective hip and knee replacement surgery (on-label indication).
2. NVAf (off-label indication before the approval, and on-label following the approval).
3. Treatment of DVT/PE (off-label indication before the approval, and on-label following the approval).
4. Any other conditions from a list of pre-defined off-label indications, including other types of surgery and history of other diseases (off-label indications). These may include but will not be limited to hip fracture surgeries, general surgeries, gynaecologic and abdominal surgeries, and diagnoses such as cancer, myocardial infarctions, other cardiac conditions, and other hypercoagulable states in which apixaban could be used off-label.

5. Patients who have no evidence of the conditions for on-label use and who cannot be assigned to the list of pre-defined off-label uses will be classified as off-label and unknown.

The only available primary data is from patients in Västra Götaland County. Primary care data may contain information on the conditions that are used to classify on-label or off-label apixaban use. A sensitivity analysis will compare the proportion of on-label users based on both primary care and hospital data to the proportion of on-label use when only the hospital data is used among those in Västra Götaland County. This assumes that the availability of GP data is not related to the ratio of on-label or off-label use and that Västra Götaland County is representative of all of Sweden.

Second, descriptive analyses will be performed in each of the indication strata to summarize:

1. Demographic characteristics of patients and prescriber specialty.
2. Estimated duration of apixaban treatment and dosages used.
3. Concomitant medication use, with the focus on contra-indicated medications.
4. History of treatment with other anticoagulants.
5. Select co-morbid conditions/medical history, such as renal impairment, severe hepatic impairment, congenital or acquired bleeding disorders.

For off-label indication strata, distribution of surgical procedures and diagnoses that patients had prior to receiving apixaban to infer possible indications that apixaban was used for. For instance, counts and proportions of patients who had other orthopaedic surgery (eg, hip fracture), within 30 days of apixaban prescription will be reported.

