## 6.2. Data Compilation Procedure

Patients who received a dispensation for apixaban (identified by ambulatory prescriptions by general practitioner or specialist physician) will be identified. The personal identification numbers of these patients will be used to link to their hospital records.

Hip and knee replacement and other surgeries will be identified via appropriate procedure codes and ICD-10 codes from hospital discharge diagnoses. The following algorithm will be used to identify the patients who have undergone the elective hip or knee replacement surgery:

- First, procedure codes will be used to identify all patients who have undergone hip or knee replacement surgery within 30 days before apixaban prescription (including total and partial replacement procedures).
- Second, hospital discharge diagnoses (both primary and secondary) will be used to see if these included hip or knee fracture diagnostic codes.
  - If yes, then the hip or knee replacement surgery will be considered non-elective and apixaban prescription off-label.

If the primary or secondary discharge diagnoses do not include hip or knee fracture, then surgery will be considered elective and apixaban prescription on-label.

NVAF and treatment of DVT/PE will be identified by ICD-10 diagnosis codes in the main or secondary discharge diagnoses as well as in hospital outpatient visits and, where available, the primary care diagnoses.

[figure not shown]

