#### **10.2. Limitations:**

- The study is based on outpatient prescriptions. Therefore patients who receive apixaban only during hospital stay (either for the approved indication or for any off-label indication) and do not refill following discharge will not be included. This limitation will be addressed by the Netherlands study where inpatient medication use data are available from the inpatient pharmacy database covering a population of over 1 million patients from a representative sample of hospital pharmacies.
- Diagnoses are retrieved from hospital discharge records (nationwide), outpatient clinic contacts (nationwide) and primary care records (available for one county only, see above). Therefore, information on possible indications may in some cases be missing.
- Validation of the data in the database by reviewing individual patients' original medical records will not be possible.
- This study is based on medical records data being collected by the relevant government agencies and county health administrations in Sweden and then accessed by the investigators for analyses. As a result, any unforeseen delay in the collection and compilation of data by one or more of the agencies is beyond the control of the Sponsor and may affect the study timeline.

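### Section 7.2 takes possible off-label indications from hospital discharges alone, passing over hospital outpatient diagnoses that the study already retrieves

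*Protocol*

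**What the plan says.** The first paragraph of Protocol Section 7.2 sets a two-step rule for off-label users.

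- Step 1: "From the hospital discharge records, the comorbidities and clinical procedures (e.g., surgeries) at the time of or within 30 days prior" to the off-label use are tabulated as its possible indications.
- Step 2, if step 1 yields no reason: "information from previous discharges will also be tabulated according to the most recent diagnosis". No look-back limit is given.

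Elsewhere the protocol describes a second nationwide source of diagnoses.

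- Section 6.1: "Since 2001, it is also possible to collect the same information from visits to hospital outpatient offices". It adds that other diagnoses in patients admitted "without knee or hip replacement or visiting hospital outpatient offices will also be retrieved".
- Section 6.2 finds NVAF and DVT/PE in main or secondary "discharge diagnoses as well as in hospital outpatient visits and, where available, the primary care diagnoses".
- Section 6.4 lists as a data element "Outpatient hospital office visit information: date of visit, ICD-10 diagnosis codes, department type".
- Section 10.2: "Diagnoses are retrieved from hospital discharge records (nationwide), outpatient clinic contacts (nationwide) and primary care records", the last for one county only.

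The last paragraph of Section 7.2 returns to the off-label strata and plans the "distribution of surgical procedures and diagnoses that patients had prior to receiving apixaban to infer possible indications that apixaban was used for". It names no source.

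**The concern.** The study is about drugs dispensed outside hospital, and its first objective concerns outpatient users. A hospital outpatient visit is a natural place for such a prescription to start. Section 7.2 nevertheless looks for the reason only in discharges, and when a recent discharge gives none it goes further back in the same source instead of turning to recent outpatient visits.

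Take an off-label user seen for cancer at a hospital outpatient clinic shortly before the first prescription, with no discharge in the preceding 30 days and one admission years earlier for something else. Under the rule this patient is tabulated under the old admission. With no earlier admission, no possible indication is found, although the relevant code is in the extracted file.

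At stake is the description of what apixaban is used for off-label. Section 1.1 gives use outside the indications as the reason for the study. A discharge-only table would lean towards inpatient surgery and older conditions, and it would rest on a narrower source than the one used for NVAF and DVT/PE.

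**Working it through.** The point is textual, so the passages are compared first. The arithmetic after that is illustration only.

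**1. Could discharge records be meant to include outpatient visits?** The protocol keeps them apart whenever it lists sources. Section 10.2 names them as two nationwide sources, and Section 6.2 joins them as one in addition to the other. Section 6.4 gives them separate bullets, and Section 6.1 introduces outpatient visits as a later addition to what is collected at discharge. Read consistently, the term in the first paragraph of Section 7.2 excludes outpatient visits.

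**2. Sources by task**

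| Task | Discharges | Hospital outpatient visits |
|---|---|---|
| NVAF and DVT/PE (6.2) | yes | yes |
| Possible off-label reasons, first paragraph of 7.2, 30-day step | yes | not named |
| Same, fallback step | yes, earlier ones | not named |
| Possible off-label reasons, last paragraph of 7.2 | source not stated | source not stated |
| Off-label list and unknown category (7.2, items 4 and 5) | source not stated | source not stated |

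Two analysts, one following the first paragraph of Section 7.2 and one the last, could produce different tables.

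**3. How old can a fallback diagnosis be?** Section 7.2 sets no limit, and Section 6.1 says that diagnoses may reach back to 1997. That is the outer bound, not the typical age, because the most recent diagnosis is taken.

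**4. Size.** The protocol gives no count of off-label users whose recent reason stands only in an outpatient record, so the effect cannot be computed. For scale, take N = 19,000 and 25% off-label use from Section 7.1 and Table 2.

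- The plan's own figure there reproduces. The 95% CI width is 2 × 1.96 × √(0.25 × 0.75 / 19,000) = 1.23 percentage points, stated as 1.2. The present point does not depend on it.
- Off-label users: 19,000 × 0.25 = 4,750.
- Assume that 10% to 50% have their recent reason only in an outpatient visit: 4,750 × 0.10 = 475, and 4,750 × 0.50 = 2,375.
- Assume that 30% to 70% of these have an older discharge: 475 × 0.30 ≈ 140, and 2,375 × 0.70 ≈ 1,660 would be tabulated under the older diagnosis. The rest would have no possible indication.
- With the same 10% to 50%, but 5% off-label use (950 users), the number passed over is 95 to 475. At 45% (8,550 users) it is 855 to 4,275.

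The off-label percentages are illustrative rows of Table 2, and the other shares are assumptions without support in the protocol.

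**The case against.** The strongest reply is that this is loose wording, not a decision to ignore outpatient data. Sections 6.1, 6.4 and 10.2 all provide for those data, the last paragraph of Section 7.2 carries no restriction, and Section 6.4 leaves operational definitions to a statistical analysis plan that is not at hand. Much of this stands. A reader might infer that the whole protocol confines off-label reasons to discharges, and it does not. But the first paragraph of Section 7.2 does name a source and a fallback. That is a stated rule at odds with the rest of the protocol, not a detail left open.

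Other stronger readings are tempting and are not supported:

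- *Recent reasons are replaced by stale ones.* A recent discharge reason is never displaced. The fallback applies only when the 30-day window gives none, and it takes the most recent diagnosis. Only recent outpatient reasons are passed over.
- *The unknown category is inflated.* Items 4 and 5 of Section 7.2 define that category and name no source. Inflation follows only if the discharge-only rule is applied to them too.
- *Outpatient cardiology patients are lost.* Patients with NVAF or DVT/PE, including those treated before approval, have their own strata, identified with outpatient data. The gap concerns other conditions.
- *Most off-label users are affected.* Counting everyone without a discharge in the previous 30 days would include patients started in primary care, whose diagnoses the national register does not hold, and pre-approval NVAF and DVT/PE patients, whose reason is captured. Section 10.2 already admits that indications may be missing.

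**Conclusion.** The point holds in limited form and should be corrected. Applied as written, the first paragraph of Section 7.2 passes over recent hospital outpatient diagnoses that the study already has. It puts the affected off-label users under an older discharge or leaves them without a possible indication. It also disagrees with the last paragraph of the same section.

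The consequence is confined to the descriptive table of possible off-label reasons, which serves the second objective. A reader might infer that the on-label proportion is biased as well. It is not changed by this rule, because Section 6.2 uses outpatient diagnoses for NVAF and DVT/PE.

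The size is unknown. The range of 475 to 2,375 patients rests on 25% off-label use among 19,000 and on an assumed 10% to 50% with an outpatient-only recent reason. It shows scale and is not an estimate.

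**What to change.** In the first paragraph of Section 7.2:

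1. Name hospital discharge records and hospital outpatient visits together as the source, both for the 30-day window and for the fallback.
2. Take the most recent contact of either type.
3. Report the time from any fallback diagnosis to the apixaban prescription, so that the reader can judge how plausible it is as a reason.
4. Use the same source wording in the last paragraph of Section 7.2, so that the tabulation is described in one way.

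The cost is about one sentence of protocol text and a rerun of the same code. Visit dates and ICD-10 codes for outpatient visits are already a planned data element in Section 6.4, so no new extraction is needed. The change will not recover reasons recorded only in primary care outside the one county with such data; Section 10.2 already covers that limitation.
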